2.4.2 Prior, concomitant and post therapies

Medications will be identified using Novartis Drug and Therapy Dictionary (NovDTD) including Anatomical Therapeutic Chemical (ATC) code. Prior and concomitant treatments will be summarized by treatment group for the safety set unless otherwise specified. Concomitant treatments will be displayed for the treatment period 1 and entire treatment period.

Prior and concomitant medications will be summarized by treatment group in separate tables. Medications will be presented in alphabetical order, by ATC codes and grouped by *anatomical main group* (the 1st level of the ATC codes). Tables will also show the overall number and percentage of subjects receiving at least one drug of a particular ATC code and at least one drug in a particular anatomical main group.

Prior medications are defined as drugs taken and stopped prior to the first dose of study treatment. Any medication given at least once between the day of first dose of randomized study treatment, and last dose plus 84 days or last visit whichever occurs earlier will be a **concomitant** medication, including those which were started pre-baseline and continued into the treatment period.

Summaries of prior and/or concomitant psoriasis specific medication will be presented as in [Table 2-5](#), but as well for topical, phototherapy and photochemotherapy (yes/no) using the randomized set.

In addition, medical procedures and significant non-drug therapies as coded in MedDRA will be summarized.

Prior or concomitant medication will be identified based on recorded or imputed start and end dates of medication taken.

2.5 Analysis of the primary objective

2.5.1 Primary endpoint

The co-primary endpoints are PASI 75 response and IGA 0 or 1 response at Week 12. The analysis of the primary variables will be based on the FAS.

2.5.1.1 Definition of PASI and related variables

The investigator or trained qualified designee will complete the PASI assessments. Whenever possible, the same evaluator should perform this assessment at all visits.

The total BSA affected by plaque-type psoriasis will be estimated from the percentages of areas affected, including head, trunk, upper limbs and lower limbs (see below for PASI assessment). The following calculations will be done: each reported percentage will be multiplied by its respective body region corresponding factor (head = 0.1, trunk = 0.3, upper limbs = 0.2, lower limbs = 0.4). The resulting 4 percentages will be added up to estimate the total BSA affected by plaque-type psoriasis. The PASI scoring system is further described in [Table 2-6](#).

A PASI score ([Fredriksson and Pettersson 1978, Weisman et al 2003, Gottlieb et al 2005](#)) will be derived as indicated in [Table 2-6](#). The head, trunk, upper limbs and lower limbs are assessed separately for erythema, thickening (plaque elevation, induration), and scaling (desquamation). The average degree of severity of each sign in each of the four body regions is assigned a score of 0-4. The area covered by lesions on each body region is estimated as a percentage of the total area of that particular body region. Further practical details help the assessment:

1. The neck is assessed as part of the head.
2. The axillae and groin are assessed as part of the trunk.
3. The buttocks are assessed as part of the lower limbs.

4. When scoring the severity of erythema, scales should not be removed.

Because the head and neck, upper limbs, trunk and lower limbs correspond to approximately 10%, 20%, 30% and 40% of the body surface area, respectively, the PASI score will be calculated using the formula:

$$\text{PASI} = 0.1 (E_h + I_h + D_h)A_h + 0.2 (E_u + I_u + D_u)A_u + 0.3 (E_t + I_t + D_t)A_t + 0.4 (E_l + I_l + D_l)A_l,$$

where E, I, D, and A denote erythema, induration, desquamation, and area, respectively, and h, u, t, and l denote head, upper extremities, trunk, and lower extremities, respectively (see [Table 2-6](#)).

PASI scores can range from a lower value of 0, corresponding to no signs of psoriasis, up to a theoretic maximum of 72.0.

The investigator is responsible for collecting the components or scoring signs and total regional area for all visits. PASI and total BSA calculations will be done by investigator at screening and randomization only; The PASI scores after randomization will be calculated by Novartis and will be used in the analysis and for derivation of PASI response values (see below).

Table 2-5 The PASI scoring system

Body region	Erythema (E)	Thickening (plaque elevation, induration, I)	Scaling (desquamation, D)	Area score (based on true area %, A)*
Head (H) [†]	0=none	0=none	0=none	0 = no involvement
	1=slight	1=slight	1=slight	1 = >0-<10%
	2=moderate	2=moderate	2=moderate	2 = 10-<30%
	3=severe	3=severe	3=severe	3 = 30-<50%
	4=very severe	4=very severe	4=very severe	4 = 50-<70% 5 = 70-<90% 6 = 90-100%
Trunk (T) [‡]	0=none	0=none	0=none	0 = no involvement
	1=slight	1=slight	1=slight	1 = >0-<10%
	2=moderate	2=moderate	2=moderate	2 = 10-<30%
	3=severe	3=severe	3=severe	3 = 30-<50%
	4=very severe	4=very severe	4=very severe	4 = 50-<70% 5 = 70-<90% 6 = 90-100%
Upper limbs (U)	0=none	0=none	0=none	0 = no involvement
	1=slight	1=slight	1=slight	1 = >0-<10%
	2=moderate	2=moderate	2=moderate	2 = 10-<30%
	3=severe	3=severe	3=severe	3 = 30-<50%
	4=very severe	4=very severe	4=very severe	4 = 50-<70% 5 = 70-<90% 6 = 90-100%
Lower limbs (L) [§]	0=none	0=none	0=none	0 = no involvement
	1=slight	1=slight	1=slight	1 = >0-<10%
	2=moderate	2=moderate	2=moderate	2 = 10-<30%
	3=severe	3=severe	3=severe	3 = 30-<50%
	4=very severe	4=very severe	4=very severe	4 = 50-<70% 5 = 70-<90% 6 = 90-100%

* Percentage (not score) of body region (not whole body) affected will be entered in the eCRF.

[†] Neck is assessed as part of the Head (H) body region.

[‡] Axillae and groin are assessed as part of the Trunk (T) body region.

[§] Buttocks are assessed as part of the Lower limbs (L) body region.

The following definitions are possible efficacy evaluations that can be used in clinical trials in psoriasis ([CHMP/EWP/2454/02, 2004](#)):

- **PASI 50 response:** subjects achieving $\geq 50\%$ improvement (reduction) in PASI score compared to baseline are defined as PASI 50 responders
- **PASI 75 response:** subjects achieving $\geq 75\%$ improvement (reduction) in PASI score compared to baseline are defined as PASI 75 responders
- **PASI 90 response:** subjects achieving $\geq 90\%$ improvement (reduction) in PASI score compared to baseline are defined as PASI 90 responders
- **PASI 100 response / remission:** complete clearing of psoriasis (PASI=0)

2.5.1.2 Definition of IGA mod 2011 score and IGA mod 2011 0 or 1 response

The IGA mod 2011 rating scale for overall psoriatic disease (shown in [Table 2-6](#)) has been developed based on a previous version of the scale used in secukinumab phase II studies, and has been updated in collaboration with health authorities (in particular the FDA). The explanations/descriptions of the points on the scale have been improved to ensure appropriate differentiation between the points. It is recommended that the same evaluator conducts the assessments throughout the study whenever possible.

The IGA mod 2011 used in this study is static, i.e., it refers exclusively to the subject's disease state at the time of the assessments, and does not attempt a comparison with any of the subject's previous disease states, whether at baseline or at a previous visit.

Table 2-6 The IGA mod 2011 rating scale

Score	Short Description	Detailed Description
0	Clear	No signs of psoriasis. Post-inflammatory hyperpigmentation may be present.
1	Almost clear	Normal to pink coloration of lesions; no thickening; no to minimal focal scaling.
2	Mild	Pink to light red coloration; just detectable to mild thickening; predominantly fine scaling.
3	Moderate	Dull bright red, clearly distinguishable erythema; clearly distinguishable to moderate thickening; moderate scaling.
4	Severe	Bright to deep dark red coloration; severe thickening with hard edges; severe / coarse scaling covering almost all or all lesions.

Note: Involvement of nails is not part of the assessment.

Subjects require an IGA mod 2011 score at randomization of 3 or 4 in order to participate in the study. Based on this scale, subjects will be considered as **IGA mod 2011 0 or 1 responder** if they achieve a score of 0 or 1 and improve by at least 2 points on the IGA mod 2011 scale compared to baseline.

2.5.1.3 Overview of analysis methods of efficacy variables

An overview of statistical analyses and methods applied to psoriasis efficacy variables is given in [Table 2-7](#).

Table 2-7 Overview of analysis methods for efficacy variables

Variable(s)	Summary statistics for binary/ categorical data	Logistic regression	Summary statistics for continuous data	Time-to-event analysis	Graphs
PASI 75 response @ Week 12	X	X			X*
IGA 0/1 response @ Week 12	X	X			X*
PASI 90 response @ Week 12	X	X			X*
PASI 50/75/90/100 and IGA 0/1 response over time	X	X			X**

Variable(s)	Summary statistics for binary/ categorical data	Logistic regression	Summary statistics for continuous data	Time-to-event analysis	Graphs
PASI score over time			X		X**
IGA mod 2011 categories over time	X				
Device usability (IFU and use-related hazards)	X				
SIAQ			X		
DLQI score over time			X		
DLQI 0/1 over time	X				

* dot plot; ** time course plot

2.5.2 Statistical hypothesis, model, and method of analysis

The co-primary endpoints of this study are PASI 75 response and IGA mod 2011 0 or 1 response at Week 12.

The statistical hypothesis is that secukinumab 300 mg (2 mL AI) is not superior to placebo with respect to the proportion of subjects with PASI 75 response and IGA mod 2011 0 or 1 response at Week 12.

Let p_j denote the proportion of PASI 75 responders at Week 12 for treatment group j and r_j denote the proportion of IGA mod 2011 0 or 1 responders at Week 12 for treatment group j, $j = 1, 0$ where,

- 0 corresponds to placebo
- 1 corresponds to secukinumab 300 mg (2 mL AI)

The following hypothesis will be tested:

- $H_1: p_1 - p_0 \leq 0$ versus $H_{A1}: p_1 - p_0 > 0$,
- $H_2: r_1 - r_0 \leq 0$ versus $H_{A2}: r_1 - r_0 > 0$

In other words:

H_1 : Secukinumab 300 mg (2 mL AI) is not superior to placebo with respect to PASI 75 response at Week 12

H_2 : Secukinumab 300 mg (2 mL AI) is not superior to placebo with respect to IGA mod 2011 0 or 1 response at Week 12

The primary analysis method will be the logistic regression with treatment group (secukinumab 2mL AI vs Placebo); baseline bodyweight strata and baseline PASI score as explanatory variables. Odds ratios will be computed for comparisons of secukinumab dose regimen versus placebo utilizing the logistic regression model fitted. In case of the logistic regression does not converge due to low response rates in the placebo group, an exact logistic regression will be performed and the detailed analysis is described in Section 4.2.3. In case of response rates of 0% or of 100% in one of the treatment groups, confidence intervals and p-values from the t-test for the risk difference comparing to 0 will be provided for the analyses using multiple imputation; for the analyses using non-responder imputation, Fisher's exact test will be performed and confidence intervals for risk difference will be provided.

If logistic regression model does not converge the following steps will be performed:

1. Run the PROC GENMOD procedure with EXACT statement;
2. If convergence not reached, remove the covariates from the model one by one until convergence is reached; start with continuous covariates (baselines PASI score), followed by removing categorical covariates (i.e., weight stratum etc.,);
3. If convergence not reached, perform Fisher's exact test.

The hypotheses H_1 and H_2 will both be tested at level 2.5% (one-sided), and significant results will only be achieved if both tests are rejected. If only one hypothesis is rejected and the other hypothesis is not rejected, superiority of secukinumab 300 mg (2 mL AI) has not been demonstrated.

Summary statistics and figures will be provided as described in [Section 5.4.2](#). Details in sensitivity analysis are provided in [Section 2.5.4](#).

2.5.3 Handling of missing values/censoring/discontinuations

Response variables based on PASI score and IGA mod 2011 categories will be imputed with multiple imputation (MI) as primary imputation method for the missing values.

Multiple imputation (MI) is a simulation based approach where missing values are replaced by multiple Bayesian draws from the conditional distribution of missing data given the observed data and covariates, creating multiple completed data sets. These completed data sets can then be analyzed using standard methods. Within this analysis the PASI score or IGA mod 2011 categories will be imputed and response variables will be derived based on the imputed scores. In the multiple imputation analysis the response status will be imputed based on the individual treatment arm information.

(Modified) Non-responder imputation will be used as a sensitivity method: Missing values with respect to response variables based on PASI score and IGA 2011 categories will be imputed with non-response regardless to the reason for missing data (e.g. premature study discontinuation, missed visit, administrative issues), exceptions will apply to the following:

- If a subject dropped out of the study prior to last scheduled visit and being responder consecutively at least for two preceding visits, the subject will be imputed as responder after discontinuation and up to the last scheduled visit.
- If a subject who was responder at visit $x-1$ and visit $x+1$ but has missing data at visit x , then the subject will be imputed as responder for visit x as long as the distance between the scheduled visits $x-1$ and x is 4 weeks or less, and the distance between the scheduled visits x and $x+1$ is 4 weeks or less. Otherwise missing data will be imputed with non-response.

Some examples are illustrated below:

Visit	1	2	3	4	5	6	7	8	9	10
Pat										
A	R	NR	R		NR	NR	NR	NR	NR	NR
A imp										
B	NR	R	R		R	R	R	R	R	R
B imp										
C	R	NR	R		NR	NR	R	R	R	NR
C imp										

Summary tables for PASI scores and IGA mod 2011 categories will be imputed using MI. The mean for PASI score and the number (%) for IGA mod 2011 categories as well as their 95% confidence intervals will be given. In addition, PASI scores and IGA mod 2011 categories based on LOCF imputation will be provided in summary tables and listings.

Note: Only PASI and IGA mod 2011 based response variables are imputed with multiple imputation or non-response, other response variables (e.g. DLQI 0 or 1 achievement) will be imputed with LOCF.

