12.4.3 Handling of missing values/censoring/discontinuations

The following imputation methods will apply to the missing data:

- Response variables based on PASI score and IGA mod 2011 categories will be imputed with multiple imputations (MI) method as primary imputation method. MI is a simulation based approach where missing values are replaced by multiple Bayesian draws from the conditional distribution of missing data given the observed data and covariates, creating multiple completed data sets. These completed data sets can then be analyzed using standard methods. Within this analysis the PASI score or IGA mod 2011 categories will be imputed and response variables will be derived based on the imputed scores. In the multiple imputation analysis the response status will be imputed based on the individual treatment arm information.
- Non-responder imputation will be used as sensitivity method: Missing values with respect to response variables based on PASI score and IGA mod 2011 categories will be imputed with non-response regardless to the reason for missing data (eg, premature study discontinuation, missed visit, administrative issues), exceptions will apply to the following:
 - If a subject dropped out of the study prior to last scheduled efficacy assessment and being responder consecutively at least for two preceding visits, the subject will be imputed as responder for the last scheduled visit.
 - If a subject who was responder at visit $x-1$ and visit $x+1$ but has missing data at visit x , then the subject will be imputed as responder for visit x as long as the distance between the scheduled visits $x-1$ and x is 4 weeks or less, or the distance between the scheduled visits x and $x+1$ is 4 weeks or less. Otherwise missing data will be imputed with non-response.

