2.5.4 Supportive analyses

Sensitivity analyses will be performed as follows:

(A) Co-primary endpoints (PASI 75 and IGA 0 or 1 response at Week 12) and key secondary endpoints will be evaluated using the logistic regression as described in primary analysis method with non-responder imputations instead of multiple imputation for missing values.

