3.1 Primary endpoint (co-primary endpoint)

With respect to the co-primary endpoint (PASI 75 response and IGA mod 2011 0 or 1 response at Week 12), the type-I-error will be 2.5% one-sided for comparison. With 40 subjects per group and assuming a response rate of 8% for PASI 75 response and IGA mod 2011 0 or 1 response in the placebo group, the power to show a response rate of 62% for PASI 75 response and 55% for IGA mod 2011 0 or 1 response in the secukinumab 300 mg (2 mL auto-injector s.c.) group based on Fisher's exact test (nQuery Advisor 7.01, two group Fisher's-exact test of equal proportions) is above 99% for PASI 75 response and IGA mod 2011 0 or 1 response.

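### The only missing-data sensitivity analysis at Week 12 counts some dropouts as responders, so it is a weak check on the multiple imputation, and the SAP and protocol state its rules differently

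*SAP*

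**What the plan says.** **Primary method.** Missing PASI and IGA values are multiply imputed, separately by treatment group (Protocol 12.4.3; SAP 2.5.3 and 5.4.4).

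**Sensitivity analysis.** SAP 2.5.4 has one item. The logistic regression for the co-primary and key secondary endpoints is repeated "with non-responder imputations instead of multiple imputation for missing values". Protocol 12.4.4 plans the same for the co-primary endpoints.

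**Its rules.** SAP 2.5.3 labels the method as modified; SAP 2.5.4 and the protocol do not. In both documents a missing response is by default a non-response, irrespective of why it is missing. There are two exceptions.

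- *Dropout after two or more consecutive responder visits.* SAP 2.5.3: "the subject will be imputed as responder after discontinuation and up to the last scheduled visit". Protocol 12.4.3: "the subject will be imputed as responder for the last scheduled visit".
- *A missing visit between two responder visits* is filled as a response, depending on the distance to each neighbouring visit. The SAP condition reads "is 4 weeks or less, and the distance between the scheduled visits"; the protocol condition reads "is 4 weeks or less, or the distance between the scheduled visits".

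SAP Section 4, which records departures from the protocol analyses, lists two removed analyses (maximum laboratory change and the stratified DLQI testing). It says nothing about the imputation rules.

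**The concern.** Multiple imputation within arm assumes that a subject with missing data would have behaved like similar subjects in the same arm who were observed. A sensitivity analysis is useful if it replaces that assumption with a less favourable one. Non-responder imputation normally does so, because every missing subject is a failure. Here, the dropouts with the best response history are counted as successes with certainty, even if they left because of an adverse event. At the planned response rates most of these subjects will be in the active arm. Agreement between the two analyses is then weaker evidence of robustness than the name suggests.

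The second issue is that the two documents do not define the same analysis. For a Period 1 dropout the difference can reach the Week 12 endpoint, and nothing states which text governs.

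**Working it through.** **1. The plan's own figure.** Inputs from SAP Section 3: "With 40 subjects per group and assuming a response rate of 8% for PASI 75 response", active rates of 62% (PASI 75) and 55% (IGA 0 or 1), and "the type-I-error will be 2.5% one-sided for comparison". The stated power "is above 99% for PASI 75 response and IGA mod 2011 0 or 1 response". Full enumeration of Fisher's exact test for two groups of 40 gives 99.97% for PASI 75 and 99.72% for IGA, so the figure reproduces. For PASI 90 at 46% against 8%, power is 97.3% (the plan says above 90%).

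**2. Direction relative to multiple imputation.** For one missing subject, multiple imputation gives a response probability between 0 and 1. The modified rule gives 1 if the subject qualifies for the dropout exception and otherwise 0, apart from the gap rule. It is therefore at least as favourable as multiple imputation for qualifying dropouts and at most as favourable for the rest. The net direction depends on the mix.

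**3. Example in the active arm.** Take 40 subjects, 4 of them missing, and 62% response among the 36 observed.

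- Strict rule: 36 × 0.62 / 40 = 22.32 / 40 = 55.8%.
- Modified rule, 62% of dropouts qualify: (22.32 + 4 × 0.62) / 40 = 24.8 / 40 = 62.0%. This equals the rate obtained if dropouts respond like completers.
- Modified rule, all 4 qualify: (22.32 + 4) / 40 = 65.8%.

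**4. Effect on the treatment difference.** With a fraction *m* missing in both arms and qualifying shares *qA* (active) and *qP* (placebo), modified minus strict = *m* × (*qA* − *qP*). The documents give neither *m* nor *q*. Setting *q* to the Week 12 planning rates:

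| Missing in both arms | PASI 75 (0.62 − 0.08) | IGA 0 or 1 (0.55 − 0.08) |
|---|---|---|
| 5% | 2.7 points | 2.4 points |
| 10% | 5.4 points | 4.7 points |
| 15% | 8.1 points | 7.1 points |

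At 10% missing the arithmetic limits are 0 points (equal shares in both arms) and 10 points (all active and no placebo dropouts qualify).

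**5. Dropout exception, side by side.** Take a subject who responds at Weeks 3 and 4, then leaves and has no later data. The SAP imputes response at every later visit, including Week 12. The protocol, read literally, imputes response only at the last scheduled visit of the study, Week 52, so the default makes Week 12 a non-response. If the protocol's last visit is instead taken to mean the last visit of the period analysed, the two agree at Week 12. The text does not say so.

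**6. Gap rule, side by side,** using the visits in SAP Table 2-3:

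| Missing visit | Gap before / after (weeks) | *and* (SAP) | *or* (protocol) |
|---|---|---|---|
| Weeks 1–3 | 1 / 1 | met | met |
| Week 4 | 1 / 4 | met | met |
| Weeks 8, 12 | 4 / 4 | met | met |
| Week 16 | 4 / 12 | not met | met |
| Weeks 28, 40 | 12 / 12 | not met | not met |

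Only Week 16 differs, and no hypothesis is tested there.

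**7. Could the conclusion change?** Under strict imputation with fraction *d* missing in both arms, each rate becomes *p* × (1 − *d*). Fisher power is then:

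| *d* | PASI 75 | IGA 0 or 1 | PASI 90 |
|---|---|---|---|
| 10% | 99.9% | 99.2% | 94.9% |
| 20% | 99.5% | 97.9% | 90.9% |
| 30% | 98.3% | 95.1% | 84.9% |

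In counts: the plan expects 40 × 0.08 = 3.2 placebo responders. With 3, Fisher's test rejects from 11 active responders (one-sided p = 0.018; with 10, p = 0.033). The plan expects 40 × 0.62 = 24.8 and 40 × 0.55 = 22.0. These figures use the planning test, not the logistic regression after imputation.

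**The case against.** The strongest defence has four parts.

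*The test is weaker, not absent.* All other missing responses still become failures: dropouts without two consecutive responses, and isolated gaps that fail the distance rule. A reader might infer that the analysis does not stress-test the result at all. The default rule contradicts that. SAP 2.5.3 also states the exceptions openly and uses the word modified.

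*Later visits are not the issue.* A reader might infer that response rates at Weeks 28 to 52 would be overstated by the carry-forward. The documents do not support this. SAP 5.4.4 assigns the by-visit summaries and regressions to multiple imputation, and SAP 2.5.4 confines the non-responder analysis to endpoints at Week 12. SAP 2.7.3 refers back to 2.5.3, but multiple imputation is primary there too.

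*Some Week 12 data will be observed.* Stopping treatment is not withdrawal from the study, and end-of-period assessments are due about four weeks after the last dose (Protocol 9.1.1). After a Week 8 dose (Day 57) that is about Day 85, inside the Week 12 window of Days 72 to 99. This limits how often the exception applies. It does not remove it: after a last dose at Week 4 (Day 29) the same visit falls near Day 57, in the Week 8 window, and subjects who withdraw consent or are lost may have no such visit.

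*No decision changes.* This stands for the significance tests under the planning rates. It does not apply to the size of the estimates, nor to the unrecorded difference between the two documents.

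**Conclusion.** The point holds in a limited form. The sole missing-data sensitivity analysis of the Week 12 endpoints is a weak check on the within-arm multiple imputation, because it can equal or exceed the estimate it is meant to challenge. The exception is the same in both arms but will mostly benefit the active arm at the planned rates.

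The effect is up to about 5 points on the PASI 75 difference between auto-injector and placebo for each 10% of subjects missing in both arms. This assumes that dropouts qualify at the Week 12 planning rates. The exception needs two consecutive responses before Week 12, and the documents give neither earlier response rates nor a dropout rate, so the size is conditional. The Week 12 significance conclusion is unlikely to change.

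The mismatch in the dropout rule matters because, read literally, it can reverse a Period 1 dropout's Week 12 value. The gap-rule mismatch is a matter of consistency and affects Week 16 only. Both should have been recorded in SAP Section 4.

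**What to change.** - In SAP 2.5.4, add a second analysis for the co-primary and key secondary endpoints in which every missing Week 12 PASI or IGA response is a non-response, without exceptions. Report it beside the existing one.
- Call the existing method modified non-responder imputation wherever it appears, including SAP 2.5.4 and Protocol 12.4.3 and 12.4.4.
- Use one dropout rule in both documents, stating explicitly whether it applies at Week 12 for subjects who leave in Period 1. Use one gap rule; the SAP's *and* is the stricter.
- List both changes in SAP Section 4.

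The cost is some wording, one more run of an existing program, and slightly lower response rates in the added sensitivity table.
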